A COMPARISON BETWEEN A STANDARDIZED (GLA:DTM CANADA) AND AN INDIVIDUALIZED (JOINTEFFORT) EXERCISE PROGRAM ON FUNCTIONAL MOBILITY, QUALITY OF LIFE, PAIN MANAGEMENT, AND INFLAMMATORY BIOMARKERS IN KNEE OSTEOARTHRITIS PATIENTS

STUDY PROTOCOL AND STATISTICAL ANALYSIS PLAN

August 30, 2018

ENCORE CATALYST AWARD APPLICATION August 2018

PRINCIPAL INVESTIGATOR: [name]

CO-PRINCIPAL INVESTIGATORS: [name], [name], [name], [name], [name], [name], [name] and [name]

TITLE: A comparison between a standardized (GLA:D[™] Canada) and an individualized (JointEffort) exercise program on functional mobility, quality of life, pain management, inflammatory biomarkers and willingness to pay in knee osteoarthritis patients.

BACKGROUND: Osteoarthritis (OA) is the leading cause of disability worldwide and affects more than 4.4 million people in Canada (13% of Canadians) [1]. OA symptoms include joint pain, stiffness, range of motion loss, and inflammation, resulting in a significant decrease in quality of life [2, 3]. Current evidencebased guidelines for OA management recommend weight loss, patient education, exercise therapy, bracing, viscosupplementation, and anti-inflammatory/pain medications prior to joint replacement surgery [4]. Unfortunately, current practice trends are not consistent with these guidelines and focus largely on joint replacement. Recently, research from a group in Denmark has shown a reduction in the progression of knee OA symptoms, joint related painkiller use, individuals on sick leave, and higher physical activity levels 12 months after a combined patient education and standardized group exercise therapy program (GLA:D®) [5-7]. Based on the Danish success, the GLA:D® program has been made available in Canada. To date it is unclear if the GLA:DTM Canada program will result in outcomes similar to those seen in Denmark, or how the GLA:DTM program compares to existing individualized OA care programs (i.e. JointEffort).

RESEARCH QUESTIONS:

- 1. Is the GLA:D[™] standardized education and exercise program associated with improvements in functional mobility, quality of life, pain management, and inflammatory biomarkers in knee OA patients in Calgary, Alberta?
- 2. Is the JointEffort individualized exercise and education program associated with improved functional mobility, quality of life, pain management, and inflammatory biomarkers in knee OA patients in Calgary, Alberta?
- 3. Do the improvements in functional mobility, quality of life, pain management, and inflammatory biomarkers in knee OA patients differ between those enrolled in the GLA:D[™] and the JointEffort education and exercise programs?
- 4. How does the cost of the programs compare to health outcomes and how much are participants willing to pay to participate in the GLA:D and JointEffort programs?

OBJECTIVES: The objectives of the proposed study are to 1) assess the association between participation in the GLA: D^{TM} standardized program and functional mobility, quality of life, pain management, and inflammatory biomarkers in knee OA patients, 2) assess the association between participation in the JointEffort individualized program and functional mobility, quality of life, pain management, and inflammatory biomarkers in knee OA patients 3) assess if there are any differences in outcomes between the standardized (GLA: D^{TM}) and individualized (JointEffort) exercise programs, and 4) Assess how the cost of the programs compare to health outcomes and how much patients are willing to pay to participate in the GLA:D and JointEffort programs.

METHODOLOGY:

Study Participants: A convenience sample of 100 participants \geq 50 years of age with a primary care physician or orthopedic surgeon knee OA diagnosis will be included in the study. Specifically, 50 individuals will participate in 1) the GLA:DTM program and 50 sex- and age-matched individuals will participate in 2) the JointEffort program. 100 participants is a conservative estimate based on the ability to detect a moderate effect between study groups (1- β =0.8, α =0.05).

Exercise Programs: The GLA:DTM program consists of 1) pre and post program outcome measurement (self-reported and functional outcomes); 2) 2 1-1.5 hour education sessions including information on OA disease characteristics, treatments and self-help strategies; and 3) a neuromuscular exercise (warm-up,

circuit training, and cool down) training program administered in 1 hour, small (up to 10 persons) groupbased, supervised sessions twice weekly for 6 weeks. The goal of the exercises is to restore neutral, functional alignment of the legs by building compensatory functional stability and improving sensorimotor control. The JointEffort program consists of: 1) one appointment aimed at individualized program design; 2) a nutritional seminar taught by a registered dietician explaining dietary recommendations for OA patients and inflammatory conditions, including weight loss and/or management; and 3) an individualized exercise (strength and neuromuscular training, balance training, and range of motion exercises) training program administered in 1 hour, small (up to 10 persons) group-based, supervised sessions twice weekly for 6 weeks.

Study Outcomes:

1) Participant Characteristics, Adherence, and Medication Use: Demographic (age, sex, height, weight, and body mass index), comorbidity, attendance, exercise log, and medication use details will be recorded at each visit. Adherence will be measured by exercise program attendance (number of sessions).

2) Self-Reported of Symptoms, Function, Quality of Life, and Cost Questionnaire: The following self-report questionnaires will be completed at baseline, 2, and 12 months: the Knee Injury and Osteoarthritis Outcome Score (KOOS) [8], the Intermittent and Constant Osteoarthritis Pain (ICOAP) Score [9], and the EuroQOL-5 Dimensions (EQ-5D-5L) Score [10]. A cost questionnaire will be used to capture information about your employment status, gross income, insurance coverage, willingness to pay, and health care visit.

3) Disease Knowledge and Arthritis-Related Self-Efficacy: The patient knowledge questionnaire on OA (PKQ-OA) [11] and the arthritis self-efficacy questionnaire [12] will be completed at baseline, 2, and 12 months.

4) Physical Function: All participants will complete the 40m Face-Paced Walk Test and the 30s Chair Stand Test [13] at baseline, 2, and 12 months.

5) Biomarker Analysis: A blood serum sample, collected at baseline, 2, and 12 months will be analyzed to assess for inflammatory biomarkers using a Discovery Assay (42 Custom-Plex human assay) with Luminex[®]xMAP technology (Eve Technologies).

STATISTICAL ANALYSIS: Descriptive statistics (mean (95% CI), proportion (95% CI) or median (range) will be used report the baseline, 2, and 12 month change in self-report, functional and biomarker outcomes, as appropriate. To account for the matched design, mean within-pair difference (95% CI) will be used to compare treatment groups across outcomes. Finally, conditional logistic regression will be used to assess the relationship between attendance (number of sessions) and 12 month change in each outcome.

SIGNIFICANCE: This project will contribute to the understanding of exercise programming prescription for knee OA patients. If GLA:DTM and/or JointEffort support improvements in functional mobility, quality of life, pain management, and inflammatory biomarkers, it could play a role in the implementation strategy for OA patients within the province. Exercise programming has the potential to be implemented in several sites across Alberta, and thus potentially modifying disease progression and possibly delaying total joint replacement.

PROJECT FLOWCHART:

Baseline Appointment Weeks 1-7 Exercise Program (GLA:D™ Canada or JointEffort)		2 Months Assessment & Questionnaires
TIME POINT	GLA:D™ Canada Group	JointEffort Group
	(Standardized Exercise Program)	(Individualized Exercise Program)
Baseline	 The GLA:D[™] Canada program will be 	1) The JointEffort program will be
Appointment	explained.	explained.
	2) Participants will be asked to complete	2) Participants will be asked to complete
	the questionnaires (KOOS, EQ-5D-5L,	the questionnaires (KOOS, EQ-5D-5L,
	ICOAP, PKQ-OA, the arthritis self-efficacy	ICOAP, PKQ-OA, the arthritis self-efficacy
	questionnaire and the Arthritis Cost	questionnaire and the Arthritis Cost
	Questionnaire Baseline).	Questionnaire Baseline).
	3) Demographics, symptoms,	3) Demographics, symptoms, comorbidities,
	comorbidities, and medication use will be	and medication use will be recorded.
	recorded. 4) Blood draw for biomarker analysis.	4) Blood draw for biomarker analysis.5) Participants will be asked to complete
	5) Participants will be asked to complete	physical function tests (40m Face-Paced
	physical function tests (40m Face-Paced	Walk Test and the 30s Chair Stand Test).
	Walk Test and the 30s Chair Stand Test).	6) Individualized program design.
Weeks 1-7	1) Two education sessions about OA (1-	1) One nutritional seminar taught by a
	1.5 hours each), including the	registered dietician explaining dietary
	degeneration process in the joint, how	recommendations for OA patients and
	the GLA:D™ Canada exercises improve	patients with inflammatory conditions, and
	joint stability, and how to retain joint	weight loss and/or weight management.
	stability through day to day self-	2) Individualized strength and
	management techniques.	neuromuscular training sessions twice a
	2) Standardized neuromuscular training	week for 6 weeks (60 minutes per session).
	sessions twice a week for 6 weeks (60	
	minutes per session).	
2 Months	1) Participants will be asked to complete	1) Participants will be asked to complete
	the questionnaires (KOOS, EQ-5D-5L,	the questionnaires (KOOS, EQ-5D-5L,
	ICOAP, PKQ-OA, the arthritis self-	ICOAP, PKQ-OA, the arthritis self-efficacy
	efficacy questionnaire and the Arthritis	questionnaire and the Arthritis Cost
	Cost Questionnaire 2-month follow up). 2) Symptoms and medication use will be	Questionnaire 2-month follow up). 2) Symptoms and medication use will be
	recorded.	recorded.
	3) Blood draw for biomarker analysis.	3) Blood draw for biomarker analysis.
	4) Participants will be asked to complete	4) Participants will be asked to complete
	physical function tests (40m Face-Paced	physical function tests (40m Face-Paced
	Walk Test and the 30s Chair Stand Test).	Walk Test and the 30s Chair Stand Test).
12 Months	1) Participants will be asked to complete	1) Participants will be asked to complete
	the questionnaires (KOOS, EQ-5D-5L,	the questionnaires (KOOS, EQ-5D-5L,
	ICOAP, PKQ-OA, and the arthritis self-	ICOAP, PKQ-OA, and the arthritis self-
	efficacy questionnaire).	efficacy questionnaire).
	2) Symptoms and medication use will be	2) Symptoms and medication use will be
	recorded.	recorded.
	3) Blood draw for biomarker analysis.	3) Blood draw for biomarker analysis.
	4) Participants will be asked to complete	4) Participants will be asked to complete
	physical function tests (40m Face-Paced	physical function tests (40m Face-Paced
	Walk Test and the 30s Chair Stand Test).	Walk Test and the 30s Chair Stand Test).

BUDGET:

1. Personnel: [name] (University of Alberta salaried time); [name] (AIHS MD/PhD Scientist-Clinician Award); [name] (University of Calgary salaried time); [name] (AHS salaried time); [name] (University of Calgary Active Living salaried time); [name] (AHS salaried time); and [name] (AHS salaried time). *Personnel Total: \$0.*

2. Program Instructors: GLA:DTM Canada Exercise Program (based on one class for 10 participants): GLA:DTM Canada Certified Instructors (physiotherapists or certified exercise physiologists): 5 x 1 hour baseline appointment @ \$75/hour = \$375.00; 2 x 1.5 hour group osteoarthritis education sessions @ \$75/hour = \$225.00; 12 x 1 hour exercise sessions @ \$75/hour = \$900.00; 2 x 1 hour follow up testing sessions at 2 months @ \$75/hour = \$150.00; 2 x 1 hour follow up testing sessions at 12 months @ \$75/hour = \$150.00. Total to run 1 GLA:DTM Canada class = \$1,800.00 (i.e. \$360.00/person). Run 5 GLA:DTM Canada classes (aim of n=10 participants per class; n=50) = \$9,000.00.

JointEffort Exercise Program (based on one class for 10 participants): JointEffort Instructors (certified exercise physiologists or certified personal trainers): 5×1.5 hour baseline appointment and program design @ \$45/hour = \$337.50; 1×1 hour group nutritional seminar @ \$75/hour = \$75.00; 11×1 hour exercise sessions @ \$45/hour = \$495.00; 2×1 hour follow up testing sessions at 2 months @ \$45/hour = \$90.00; 2×1 hour follow up testing sessions at 12 months @ \$45/hour = \$90.00. Total to run 1 JointEffort class = \$1,087.50 (i.e. \$199.50/person). Run 5 JointEffort classes (aim of n=10 participants per class; n=50) = \$5,437.50.

Program Instructors Total (5 JointEffort and 5 GLA:D[™] classes, n=100): \$14,437.50.

3. Instructor Training: GLA:D[™] Canada Training: 2 instructors x \$450 = **\$900.00**; JointEffort Training: 5 instructors

x 1 hour (testing protocols) @ \$45/hour = \$225.00. Instructor Training Total: \$1,125.00.

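### The between-program comparison of willingness to pay has no planned adjustment for income or insurance, although the groups are not randomised and both are collected

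*Combined protocol and SAP*

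**What the plan says.** - **The aim.** Research question 4 asks "how much are participants willing to pay to participate in the GLA:D and JointEffort programs", and objective 4 repeats it. The application's TITLE line announces a comparison of the two programs that ends with "inflammatory biomarkers and willingness to pay in knee osteoarthritis patients".
- **The groups.** Under Methodology, Study Participants, the plan takes "A convenience sample of 100 participants": 50 people in GLA:D and "50 sex- and age-matched individuals will participate in 2) the JointEffort program". No randomisation or other assignment rule is given, and sex and age are the only matching factors.
- **The measurement.** Study Outcomes, item 2, says the cost questionnaire covers employment status, "gross income, insurance coverage, willingness to pay, and health care visit". The Project Flowchart places this questionnaire at baseline and at 2 months and does not list it at 12 months. In each column the baseline visit begins with an explanation of that column's own program ("Canada program will be" explained in one, "The JointEffort program will be" explained in the other). The questionnaires follow.
- **The analysis.** Statistical Analysis compares the groups by the mean within-pair difference with a 95% CI. It names no covariates and gives no separate analysis for willingness to pay or cost.
- **The use.** The section on relevance and potential benefit ties exercise programming to income, out-of-pocket cost and expected benefit. It says these data will help decision-makers choose between public, partly subsidised and private funding.

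**The concern.** What a person will pay depends on what that person can pay. Matching on sex and age does not make two groups alike in income or insurance, and nothing else in the design does so. If one program enrols better-off or better-insured people, the mean within-pair difference will credit that program with a higher value even when the two are valued alike at equal income. Readers would then see a difference between programs where there is a difference between clienteles, and the result is meant to inform a funding decision. The plan itself treats income as relevant and collects it, so the gap lies in the analysis and can be closed there.

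**Working it through.** The plan gives no figure for willingness to pay or income, so there is nothing of its own to reproduce on this point. Its only sample-size figure (100 in total, 80% power, alpha 0.05, a moderate effect with no number attached) is not specific to willingness to pay, and the point does not depend on it.

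**1. Does any step of the plan balance or adjust for income?**
- Assignment: convenience sample, no randomisation described. No.
- Matching: sex and age. No.
- Analysis: mean within-pair difference, no covariates. No.
- Data collection: gross income and insurance coverage are on the cost questionnaire. Yes, but no analysis uses them.

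**2. How large could the bias be?** This is an illustration on assumed values. Put willingness to pay and income in SD units. Let r be the correlation of willingness to pay with income, taken as linear and equal in both groups, and let g be the difference in mean income between the groups.

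- Bias in the mean difference = r × g. Pairing on sex and age does not remove it, because g is whatever income gap remains after matching.
- Standard error with 50 per group and within-pair correlation 0: sqrt(2/50) = 0.20 SD.
- Chance of a two-sided 5% finding when the programs are valued alike, with k = bias/0.20: 1 − Φ(1.96 − k) + Φ(−1.96 − k).

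| r (assumed) | g (assumed) | bias = r × g | k | chance of a false finding |
|---|---|---|---|---|
| any | 0 | 0 | 0 | 5.0% |
| 0.1 | 0.2 | 0.02 | 0.10 | 5.1% |
| 0.3 | 0.5 | 0.15 | 0.75 | 11.7% |
| 0.5 | 0.5 | 0.25 | 1.25 | 24.0% |
| 0.5 | 0.8 | 0.40 | 2.00 | 51.6% |

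Against a program difference of 0.5 SD (also assumed), the bias is 0.02/0.5 = 4% to 0.40/0.5 = 80%. The range runs from negligible to serious, and nothing in the documents says where this trial would fall.

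**3. What does adjustment cost in information?** With 50 pairs, the unadjusted within-pair difference has 50 − 1 = 49 degrees of freedom. One term for income and one for insurance leave 49 − 2 = 47. If income is recorded in bands, each further band costs one more.

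**The case against.** The strongest reply is that the plan promises no such comparison. Question 4 is worded descriptively, question 3 lists the outcomes to be compared and leaves willingness to pay out, and the cover title omits it too. For a funding decision, what users would pay for their own program is a sensible quantity by itself. This narrows the point but does not remove it. The application's TITLE line does make willingness to pay a compared outcome, the stated between-group method applies across outcomes, and two group means reported side by side will be compared whatever the wording.

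The second reply is that the size is unknown. That stands: with balanced incomes the bias is zero.

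Three stronger readings are tempting, and the documents do not support them:
- **That participants choose their program.** The text says convenience sample and matched. It does not say who decides which program a person enters. Self-selection is plausible, but it is an inference.
- **That a difference would reflect income as much as the programs.** There are no income or willingness-to-pay data from which to show this.
- **That each person can give an informed value for one program only.** The flowchart lists only the person's own program as explained, but the questionnaire items are not reproduced and consent pages are not in the text reviewed. Whether the items ask about one program or both cannot be told.

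A reader might also conclude that every participant must value both programs. With all 100 people doing so, the 95% CI half-width, t(99) × sqrt(2(1 − r)/100), would be 0.23, 0.20, 0.15 or 0.13 SD at assumed within-person correlations r of 0.3, 0.5, 0.7 or 0.8. For 50 pairs, t(49) × sqrt(2(1 − ρ)/50) gives 0.40 at within-pair correlation ρ = 0 and 0.34 at ρ = 0.3. These figures describe precision, not confounding. The approach also changes what is measured, by adding a hypothetical value for a program the person will not attend. Income cancels within person only if it adds equally to both values. Describing the alternative at baseline could also affect later self-reported outcomes.

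**Conclusion.** The point holds as an omission from the analysis plan. Willingness to pay is a compared outcome by the application's TITLE line, the groups are not randomised and are matched on sex and age only, and the stated comparison leaves income and insurance unused. A between-program difference may therefore be confounded by ability to pay. The bias cannot be sized from the documents. The 0.02 to 0.40 SD range rests wholly on the assumed correlations and income gaps. The documents do not show that the elicitation design is faulty, and asking everyone about both programs is an optional design choice, not a required correction. The matter is minor for the trial as a whole, but it bears on the funding question and costs almost nothing to correct.

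**What to change.** Add to Statistical Analysis that the between-program difference in willingness to pay, at baseline and at 2 months, will be estimated as follows:
- a regression that respects the matched pairs, for example with pair as a fixed or random effect;
- adjustment for gross income and insurance coverage, both as recorded at baseline, for the 2-month comparison as well;
- the adjusted difference with its 95% CI, reported beside the unadjusted mean within-pair difference, so that readers can see how far adjustment moves it.

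State in advance how missing income answers are handled. In a complete-case analysis with fixed pair effects, one missing answer removes the whole pair from the adjusted estimate. With a random effect the other member still contributes. One sentence on how participants come to each program would also help readers judge what confounding may remain, since adjustment deals only with what was measured.

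The cost is a few degrees of freedom and the missing-data rule. No new question, visit or participant is needed.

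### No scale is named for the biomarker analysis, and a median reported with a range gives no confidence interval for within-program change

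*Combined protocol and SAP*

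**What the plan says.** The analysis plan is one paragraph, headed Statistical Analysis. For within-program results it offers three formats, "mean (95% CI), proportion (95% CI) or median (range"), to be applied to "12 month change in self-report, functional and biomarker outcomes, as appropriate". The mean and the proportion come with a confidence interval; the median comes with a range. No rule says when each applies.

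For the program comparison there is one method: "mean within-pair difference (95% CI) will be used to compare treatment groups across outcomes". No scale, transformation or rank-based alternative is given for any outcome.

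Biomarkers are part of the main questions. Research Questions 1 to 3 each include them, and question 1 asks about "functional mobility, quality of life, pain management, and inflammatory biomarkers in knee OA patients in Calgary, Alberta". Study Outcomes, item 5, has serum taken at baseline, 2 and 12 months and assayed for "inflammatory biomarkers using a Discovery Assay (42 Custom-Plex human assay"). Study Participants gives 50 people in GLA:D and "50 sex- and age-matched individuals will participate in 2) the JointEffort program", which is 50 pairs.

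**The concern.** There are two separate issues.

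**Scale of the comparison.** Marker concentrations are positive. If their distribution has a long right tail, a few high values dominate the standard deviation of the paired differences. A mean difference in concentrations then has a wide interval whose width varies greatly from sample to sample. The authors provide a median among the summaries, so they foresee outcomes for which a mean is unsuitable, but the comparison has no matching alternative.

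**Interval for within-program change.** Questions 1 and 2 ask whether each program is associated with improvement. The descriptive sentence is the only planned analysis of change within a program. A range shows how far individuals spread and tends to widen as the sample grows; it does not say how precisely the median is known. For any marker reported this way, questions 1 and 2 have no measure of uncertainty. The between-program interval does not fill the gap, because it answers question 3 only.

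At stake is the precision of the biomarker part of questions 1 to 3, and freedom to choose the summary or scale marker by marker after seeing the data.

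**Working it through.** The plan states no biomarker effect, SD or distribution, so it has no figure of its own to reproduce here. The only design input taken from it is 50 pairs.

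**Assumptions (none from the documents).** Each marker is log-normal with log-SD s and baseline median 1. Baseline and follow-up log values correlate at r = 0.7. Matching induces no correlation within pairs. One program has a true follow-up/baseline ratio g = 0.75 (a 25% reduction), the other 1. The test is a two-sided paired t-test at 5% on the difference in change.

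**Log scale.** The effect is −ln(0.75) = 0.2877. The SD of the paired difference in log change is s·√(4(1 − r)) = 1.0954·s.
- s = 0.5: 0.2877/0.5477 = 0.525; noncentral-t power with 50 pairs is 95%.
- s = 1.0: 0.2877/1.0954 = 0.263; power 44%.

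**Concentration scale.** Let V = e^(s²)(e^(s²) − 1) and C = e^(s²)(e^(r·s²) − 1). The variance of change is V(1 + g²) − 2gC in the program with the reduction and 2V − 2C in the other. The mean difference is e^(s²/2)(1 − g).
- s = 0.5: V = 0.3647 and C = 0.2456, so the variances are 0.2015 and 0.2383. SD = √0.4398 = 0.663, effect 0.2833, standardised effect 0.427. Approximate power 84%; simulation gives 85%.
- s = 1.0: V = 4.6708 and C = 2.7557, so the variances are 3.1646 and 3.8302. SD = √6.9948 = 2.645, effect 0.4122, standardised effect 0.156. Approximate power 19%; simulation gives 22%.
- s = 0.25: standardised effect 0.924 against 1.050 on the log scale; power is near 100% on both.

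The t approximation is slightly off for skewed differences, so the simulated values (8,000 to 20,000 runs) are used for the concentration scale.

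**Power for the between-program comparison, over a range of assumptions**

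| True reduction | log-SD | Concentration | Log |
|---|---|---|---|
| 15% | 0.5 | 43% | 55% |
| 15% | 1.0 | 10% | 18% |
| 25% | 0.25 | about 100% | about 100% |
| 25% | 0.5 | 85% | 95–96% |
| 25% | 0.75 | 44% | 69% |
| 25% | 1.0 | 22% | 44–45% |
| 25% | 1.5 | 8% | 23% |
| 40% | 0.75 | 83% | 99% |
| 40% | 1.0 | 50% | 91% |
| 40% | 1.25 | 27% | 73% |

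**Within-program change.** For a 25% reduction at log-SD 1.0, power is 46% on the concentration scale and 73 to 74% on the log scale. At log-SD 0.5 both exceed 99%.

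**Validity.** Over log-SD 0.25 to 1.5, the concentration-scale 95% interval for the paired difference covered the truth in 94.9% to 96.8% of runs. For the within-program mean change, coverage was 93.1% to 97.0%. What deteriorates is width: at log-SD 1.0 the ratio of the 97.5th to the 2.5th percentile of interval width is 3.1, against 1.5 on the log scale.

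**The range.** At log-SD 1.0 with no true change and n = 50, the range of individual changes had a median of 10.7 over repeated samples, with 2.5th to 97.5th percentiles of 5.1 to 28.6 (in units of the baseline median). An exact interval for the median is available: with n = 50 it runs from the 18th to the 33rd ordered value, with coverage P(18 ≤ X ≤ 32) = 96.7% for X binomial(50, 0.5).

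**The case against.** Several points on the other side stand.

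- The plan does not say that concentrations will be analysed untransformed. A mean within-pair difference of log values, back-transformed to a ratio, fits the sentence as written. The fault is that the scale is left open.
- Skewness is nowhere in the documents. Log-normal data with a proportional effect is also the model under which the log scale does best, so the table favours the remedy. With mild skew nothing is lost. With a small effect and strong skew both analyses are weak.
- Nothing in the documents supports an effect of any given size between two active exercise programs. The 40% rows are one end of a range, not an expectation.
- A mean with 95% CI is also offered for biomarkers. The interval is missing only where the median is chosen.

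A reader might go further and infer that single outlying samples could decide the result. The calculations do not support that: type I error stayed at about 3 to 5% on the concentration scale and coverage was close to nominal. Extreme values mainly widen the interval. A reader might also infer that questions 1 and 2 have no interval for any biomarker, which the first format in the plan's own list contradicts. Finally, one might ask for rules on values below assay detection limits. The documents mention neither such limits nor undetectable values, so this point does not rest on them.

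The objection does not remove the gap. One comparison rule covers every outcome without naming a scale, and a range is not an interval for a median whatever the distribution.

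**Conclusion.** The point holds in a conditional form. The missing interval for a median change can be read directly from the text and needs no simulation; it affects any marker for which that format is chosen, under questions 1 and 2. The loss from a concentration-scale mean difference depends on skewness that the documents neither state nor rule out. Under the assumptions above and a 25% reduction, it is nil in power at log-SD 0.25, about 10 percentage points at log-SD 0.5, and roughly half the power at log-SD 1.0. The harm is imprecision and missed effects, not invalid inference. The plan should be changed, because a better method is easily specified before the data are seen.

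**What to change.** In Statistical Analysis, state that biomarker change within each program and the within-pair comparison of programs will be analysed on the log scale. Report the within-program result as the geometric mean ratio of follow-up to baseline with 95% CI, and the comparison as the ratio of those ratios with 95% CI.

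For change scores, replace the median with range by the median and its 95% CI, for example the exact order-statistic interval.

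This changes wording only; no visit, sample or assay is affected. The small downside is that effects are reported as ratios instead of differences in concentration.

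### The 12-month change in each program is summarised with no missing-data method, so it rests on those measured at that visit and is biased if return depends on earlier response

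*Combined protocol and SAP*

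**What the plan says.** Objectives 1 and 2 ask about each program separately. For example, the second is to "2) assess the association between participation in the JointEffort individualized program and functional mobility, quality of life" and the other outcome domains. The Statistical Analysis section has three components:

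- **Change within a program.** Descriptive summaries "will be used report the baseline, 2, and 12 month change in self-report, functional and biomarker outcomes, as appropriate". The forms allowed are means or proportions with 95% CIs, and medians with ranges. This is the only component that addresses objectives 1 and 2.
- **Between programs.** The "mean within-pair difference (95% CI) will be used to compare treatment groups across outcomes". This serves objective 3.
- **Attendance.** The plan says that "conditional logistic regression will be used to assess the relationship between attendance (number of sessions) and 12 month change in each outcome". Here attendance is an exposure. It is not used to handle missing outcomes.

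On data collection, Study Outcomes states: "The following self-report questionnaires will be completed at baseline, 2, and 12 months". It sets the same three times for the knowledge and self-efficacy questionnaires, the function tests and the blood sample, and the Project Flowchart repeats this for both programs. Attendance is also recorded: "Adherence will be measured by exercise program attendance (number of sessions").

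The documents contain no missing-data rule, analysis set, repeated-measures model, imputation, sensitivity analysis or dropout allowance.

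**The concern.** A change score at 12 months can be computed only for someone with both a baseline and a 12-month value. Classes end by week 7, so the 12-month visit comes roughly 10 months later (12 months less about 1.6), and full retention cannot be taken for granted. If the people who return differ in response from those who do not, the mean, proportion or median change among returners is not that of everyone enrolled.

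Two features make this matter. Objectives 1 and 2 are single-group before-after estimates, so there is no comparison arm in which a shared bias could cancel. The Significance section also ties improvement in either program to provincial implementation, so the single-program estimates carry weight of their own. Meanwhile the 2-month score and the attendance count, both scheduled for everyone, are natural predictors of a missing 12-month value, and the stated method leaves them unused.

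This is about a person's own missed visit in the single-program estimates. Loss of matched partners in the between-program contrast is a separate matter.

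**Working it through.** **The plan's own figures.** The plan gives no retention, precision or bias figure for within-program change. Its one statistical figure, 100 participants, enters here only as 50 per program. With an assumed effect of 0.5 SD, 100 is reproduced one-sided (50 per arm) and closely by a two-sided matched design with pair correlation 0.2 (51 pairs), but not two-sided with independent groups (63 per arm). Nothing below depends on that.

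**Inputs.**

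- From the documents: 50 people per program; outcomes at baseline, 2 and 12 months.
- Assumed: 10-30% missing at 12 months; odds of returning 2 or 3 times higher per SD better 2-month change; correlation ρ of 2- and 12-month change 0.4-0.6.

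**Step 1: general identity.** Bias = dropout share × (returner mean − leaver mean). With 20% dropout and leavers 0.5 SD worse, it is 0.20 × 0.5 = 0.10 SD. If leavers are 0.5 SD better, it is −0.10 SD.

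**Step 2: bias when return depends on the 2-month change.** For bivariate normal changes, bias at 12 months = ρ × (mean 2-month change of returners − mean of everyone), in SD units. Simulation with 300,000 people per scenario gave the ρ = 0.5 column. Because the bias is proportional to ρ, the other columns are that column × 0.4/0.5 and × 0.6/0.5.

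| Dropout | Odds ratio | ρ = 0.4 | ρ = 0.5 | ρ = 0.6 |
|---|---|---|---|---|
| 10% | 2 | 0.026 | 0.033 | 0.040 |
| 10% | 3 | 0.039 | 0.049 | 0.059 |
| 20% | 2 | 0.051 | 0.064 | 0.077 |
| 20% | 3 | 0.074 | 0.092 | 0.110 |
| 30% | 2 | 0.076 | 0.095 | 0.114 |
| 30% | 3 | 0.108 | 0.135 | 0.162 |

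The signs reverse, with the same magnitudes, if better responders are the ones who stay away.

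**Step 3: compare with precision.** The 95% CI half-width is t(0.975, n−1)/√n in SD units: 0.300 for n = 45, 0.320 for n = 40 and 0.344 for n = 35.

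- Smallest ratio: 0.026/0.300 = 9%.
- Largest ratio: 0.162/0.344 = 47%.
- Coverage at the worst corner: bias/SE = 0.162 × √35 = 0.96, so a nominal 95% interval covers about Φ(1.96 − 0.96) − Φ(−1.96 − 0.96) ≈ 84%. At the mildest corner coverage stays near 95%.

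**Step 4: what using the 2-month data achieves.** This was checked over a wider correlation range, 0.3-0.7, with the same dropout rates and odds ratios.

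| Situation | Returner-only bias (SD) | Left after using 2-month scores (SD) |
|---|---|---|
| Return depends on 2-month change; all leavers have it | 0.02-0.19 | about 0 |
| Same, but only half of leavers have it | 0.02-0.19 | 0.01-0.08 |
| Return depends on the 12-month change itself; all leavers have 2-month scores | 0.07-0.27 | 0.03-0.25 |

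The near-zero result in the first row follows from its own premise, since dropout was generated from the variable then adjusted for.

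**The case against.** The strongest case on the other side is that much of the concern must be supplied by the reader.

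- **The plan never declares a completer analysis.** This is correct; it is inferred from silence. The inference is still sound, because a 12-month change cannot be formed without a 12-month value and no other method is given.
- **A reader might infer that 2-month scores are in hand for most leavers.** The documents do not support that. The visit is scheduled for all, but no retention figure is given, and people can leave during the classes, before the 2-month visit.
- **A reader might infer that each program's improvement is overstated.** Nothing in the documents says poor responders return less often. If people who feel well stop coming, the error runs the other way.
- **A reader might see limited access at 12 months in the budget line "2 x 1 hour follow up testing sessions at 12 months".** The budget gives the same two one-hour sessions at 2 months for both programs, so it does not show that the later visit is harder to attend. The function tests are also planned for all participants at both follow-ups, parking is budgeted for 100 people each time, and follow-up is not made to depend on finishing classes.
- **Objectives 1 and 2 name no time point.** The 2-month change is reported as well, and medians or proportions are allowed, so the questions do not rest on the 12-month mean alone. The gap nonetheless applies to any 12-month summary, whichever statistic is used.
- **The size is modest and wholly assumed.** It is below half the interval half-width even at the extreme.

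These points narrow the claim. They do not remove it: a better method exists, uses data already scheduled, and needs only to be written down.

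**Conclusion.** The point holds in conditional form. The stated descriptive summary defaults at 12 months to people measured then. It is biased for everyone enrolled whenever return depends on response, upward or downward according to who stays away. Under the assumed inputs the bias is about 0.03-0.16 SD, or 9-47% of the 95% CI half-width. At 20% dropout and correlation 0.5 it is 0.06-0.09 SD. Dropout, its direction, the odds ratio and the correlation are all assumptions; the documents supply none of them.

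A reader might go further and conclude that the data already scheduled would remove the bias. That holds only if return depends on what has been observed and leavers have their 2-month scores. Otherwise part, or most, of it stays. This is an inexpensive improvement that should be made before analysis, not a flaw that invalidates the trial.

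**What to change.** In the Statistical Analysis section, pre-specify for objectives 1 and 2:

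1. **Main estimate.** Estimate each program's 2- and 12-month change for everyone enrolled with a baseline, using a likelihood-based repeated-measures model or multiple imputation with the baseline, 2-month and 12-month values together.
2. **Attendance.** Use it as an auxiliary variable only, either in the imputation model or with estimates averaged back over everyone enrolled. It is measured after baseline, so an ordinary covariate would make the estimate conditional on attendance.
3. **Skewed outcomes.** Transform skewed biomarkers, or impute and then summarise, so that the planned medians and proportions remain available.
4. **Transparency.** Keep the completer summary as a secondary line. Show the 2-month change of 12-month returners and non-returners side by side, with the number of leavers who have a 2-month score.
5. **Sensitivity.** Add a not-at-random analysis that shifts the imputed 12-month values by a stated range in both directions. The program mean moves by the missing share times the shift: with 20% missing, a 0.5 SD shift moves it 0.10 SD.

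The cost is SAP wording and a little more analysis work, with no new data collection. The main estimate will rely on a missing-at-random assumption, which is why items 4 and 5 belong with it.
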